5. BACKGROUND AND SIGNIFICANCE

Preschool anxiety is prevalent, with 20% of children affected (Bufferd et al, 2012). Among these, a majority will continue to experience symptoms throughout adolescence and adulthood (Bittner et al, 2007). Early childhood anxiety also predisposes to a host of negative, long-term outcomes, including major depression and substance abuse (Bittner et al, 2007; Zimmerman et al, 2003), underscoring the importance of early intervention.

We will test a neuroscientifically-derived intervention targeting effortful control (EC) skills, low levels of which have been linked to greater emotional reactivity and clinical anxiety. Defined as the ability to effectively regulate behavior and emotion, EC reflects the activity of frontal brain systems and can be indexed by an event-related brain potential, the error-related negativity (ERN) and time frequency interchannel phase synchrony (ICPS) (Moran et al, 2015). The ERN is a neurophysiological response, localized to the dorsal anterior cingulate cortex, signaling the need for adaptive behavioral adjustments following errors (Gehring et al, 2018). The ICPS reflects the transmission of this error signal to the dorsolateral prefrontal cortex in order to implement the specified control (Cavanagh et al, 2009).

Findings from our labs and the work of others have shown that reduced ERN and ICPS relate to behavioral deficits in EC and enhanced threat reactivity (Lo et al, 2015) similar to that documented in clinically anxious children (Meyer, 2017). In response, our team developed a child-friendly group EC training, Camp Kidpower-Structured Games, designed to increase ERN, ICPS and related EC behaviors in the service of decreasing anxiety symptoms in preschoolers. Results of our pilot study indicate that this brief EC training approach engaged the intended EC neural and behavioral targets and reduced anxiety symptoms (Schroder et al, 2022). Building on this pilot work, the current project aims to replicate and extend these findings in a larger sample using a randomized controlled design.

The Kidpower-Structured Games condition will be tested against an active comparator "Child-led Play" condition (Kidpower-CLP). Kidpower-Structured Games will involve executive function training games, shown to improve executive function skills in preschoolers (Diamond and Ling, 2016) and tested previously for the treatment of children with ADHD (Halperin et al, 2013). Kidpower-CLP will permit identification of specific effects of the EC training by controlling for confounds including: a) participation in a fun playgroup; b) interaction with new children during activities; c) separation from parents; and d) time spent with new adults. As detailed next, Kidpower-CLP is derived from evidence based treatment for early childhood psychopathology; in this study, it will include structured play activities (art activities, dramatic play, and story time), but not EC games. Both Kidpower-Structured Games and -CLP conditions will be delivered to small groups of clinically anxious preschoolers by study team members at the same staff to child ratio.

Child-led play has been shown to foster the development of cognitive, physical, social, and emotional well-being of children (Ginsburg et al, 2007). Moreover, play is important to healthy brain development (Shonkoff and Phillips, 2000; Frost, 1998; Tamis-Lemonda et al, 2004). When play is allowed to be child driven, children practice decision-making skills, move at their own pace, discover their own areas of interest. Additionally, child-led play promotes healthy parent-child attachment. The most widely employed early childhood psychotherapy, Parent Child Interaction Therapy (PCIT), focuses on Child-led Play for the first half of treatment. During this portion of PCIT, children experience child-directed play with their parents to encourage warm, secure caregiver-child relationships (Lieneman et al, 2017). The child-led play condition in Camp Kidpower gives children the opportunity to direct their own play at camp, while training parents to deliver child-led play at-home. As such, it fosters development across cognitive, social, neural and relational domains.

6. RESEARCH DESIGN AND METHODS (1 page maximum)

Participants are randomized to a camp-style intervention ("Camp Kidpower"), which includes either EC training (Kidpower-Structured Games) or child-led playgroup (active comparator; Kidpower-CLP). Before and after the 4-week intervention, a multi-level assessment will be completed, including clinical interview with parent about their child's anxiety symptoms, parent-report surveys on child and self, lab-observed behavioral tasks and electroencephalogram (EEG) with child. Primary analyses will test for group mean differences in neurophysiological and behavioral indices of EC from time 1 (pre-intervention) to time 2 (post-intervention) among children assigned to Kidpower- Structured Games training compared to those assigned to Kidpower-CLP. Secondary analyses will test relationship of changes in neurophysiological targets with change in EC behaviors and change in anxiety severity.

The Kidpower-Structured Games were adapted from a group-based intervention originally designed to treat EC deficits in children with attention deficit hyperactivity disorder (Halperin et al, 2013) and a recently published review of executive function and effortful control interventions (Diamond and Ling, 2016). Kidpower-CLP was developed by the study team to include all of the same elements as Kidpower-Structured Games except for EC training games.

Both Kidpower-Structured Games and Kidpower-CLP will occur over 4-5 sessions, for approximately 3 hours each session. Sessions may be delivered back-to-back or over the course of four weeks. Times will be chosen to maximize child focus and energy and to provide the most convenience for families. Regardless of condition, children will begin with a group welcome activity, then will complete 1-2 of the intervention exercises for that day with their camp counselor. After a brief break and snack, children will complete the remaining 1-2 intervention exercises with their camp counselor, then come back together for a final group activity. The last 30 minutes of camp will include parents, who will be assigned daily homework involving the same play as at camp to complete with their child in between camp sessions. Two parent meetings (led by the lead camp counselor) will take place; the first will occur prior to the beginning of camp to orient parents, and the second will be held mid-way through camp to answer questions that may have arisen.

Error-eliciting Zoo Task: The "Zoo task", a "Go/No-Go" paradigm assessing effortful control, has been found to reliably elicit ERN in preschoolers (Grammer et al, 2014). Before performing the task, children are instructed to help the game's zookeeper find all the escaped animals. Children then view a series of animals on a computer screen and are asked to press a button when a new animal appears (Go trials), unless the animal is an orangutan (i.e., inhibit button response,

No-Go trials). The task includes 8 blocks, each containing 30 unique animals (Go trials) and 10 orangutans (No-Go trials) in random order.

Error Related Negativity (ERN): As children play the Zoo task, EEG data will be recorded from 32 scalp sensors embedded in an elastic cap using the BioSemi Active 2 system (Amsterdam, The Netherlands). ERPs from fronto-central recording sites time-locked (within 100 ms) to error and correct response will be examined. Differentiation between these trial types is the primary ERN measure, but we will also consider ERN on error trials, as well as ERPs on correct trials separately. Previous research indicates that the ERN demonstrates good psychometric properties across children, adolescents and adults. The number of NoGo errors and response times (RTs) to Go trials will also be considered in NP analyses, as performance can affect ERN amplitude.

Time Frequency Interchannel Phase Synchrony (ICPS): Using the same approach previously employed by our group, complex time-varying energy time-frequency distributions (TFDs) of all the EEG signals at each channel extracted from the Zoo task (described above) will be obtained using the reduced interference distribution (RID) Rihaczek distribution. RID based TFDs offer improved time-frequency support relative to wavelets. Functional connectivity will be assessed using interchannel phase synchrony (ICPS), based on the phase locking value (PLV), derived from the RID TFDs. Current source density (CSD) transform will be applied to EEG data before phase synchrony analysis to reduce volume conduction, using published methods. We will focus on ICPS within the theta band in the ERN time window. Consistent with previous work, the current study will report ICPS between FCz and lateral frontal sites, indexing mediolateral functional connectivity, indexing control processing.

Behavioral Measures: Pre/post behavioral tasks are drawn from widely employed temperament protocols - e.g., Lab-TAB, Kochanska battery (Kochanska et al, 1996), and the age-normed NIH Toolbox (Zelazo et al, 2013). In addition to these tasks, free play time will be given to children and parent during the session. Behavioral tasks will be videotaped (if consent is given) for analysis. Behavioral tasks total approximately 2 hours per visit.

While completing select behavioral tasks (potential threat task, speech task, and bubbles task) (McGinnis et al, 2016), children may be asked to wear a lab-owned smartphone attached to a belt that will be worn around the child's waist. The smartphone uses a custom program, designed specifically for this research application/data collection and is not publicly available. It will guide administrators through the tasks by prompting them to press a 'start' and 'stop' button for data collection. It stores raw motion and audio data from the smartphone's accelerometer and microphone, labeled only with a de-identified numeric ID. The smartphone will not be connected to either cellular or wireless networks during data collection. This de-identified data will be transferred to the secure servers via physical wire and immediately deleted from the device after each lab visit. Motion and audio data on tasks are especially helpful for generating behavioral indices of fear. In the potential threat task, children walk besides experimenter towards a covered terrarium, and motion data indexes reluctance to approach-- a behavioral correlate of Fear. In the speech task, audio data can be submitted to machine learning algorithms to discern speech patterns associated with anxiety severity. Motion and audio data during the Bubbles task will be used to generate a behavioral index of Reward.

Clinical Measures: May include a combination of clinician-assessed and clinical self-report measures for child anxiety and depression, temperament, development, intelligence, and parent psychopathology and experiences. These may be administered during screening, at either of the lab visits, and/or during the follow-up phone call. Questionnaires may be administered via paper forms or via online via a secure application such as Qualtrics. A summary of measures and timing for administration is included in the Uploads section.

Data collected in the current study will be collapsed together with data collected using the same study protocol at Michigan State (N = 71), New York State Psychiatric Institute (N = 43) to test study aims.

In the current study, up to 20 participants will be enrolled at the Columbia University Site. The Michigan State University site has completed enrollment and will assist in data analysis.

7. RESEARCH PARTICIPANTS (2-3 paragraph maximum)

Children with clinical anxiety symptoms aged 4-5.99 years old

This study will examine the mechanistic plausibility of EC training for childhood anxiety, promoting developmental trajectories towards positive mental health.

Inclusion criteria

1. Participants must be 4.0-5.99 years old at time of consent.
2. Has primary clinical diagnosis of separation anxiety disorder, social anxiety disorder, generalized anxiety disorder, panic disorder, obsessive-compulsive disorder, and/or specific phobia if symptoms present more days than not.
3. Written informed consent by a parent/legal guardian.
4. Fluent in English (note: participant may be bilingual, but must be able to speak and understand fluent English to participate in study.)

Exclusion criteria

1. History of head injury
2. History of serious neurological illness or current medical illness
3. History of major depressive disorder (MDD)
4. History of post-traumatic stress disorder (PTSD)
5. History of neurodevelopmental delay, autism spectrum disorder (ASD), or intellectual disability
6. Currently taking medications that affect the central nervous system (e.g., stimulants for ADHD, SSRIs for anxiety/depression, alpha agonists for ADHD or tics).
7. Currently receiving psychotherapy or other behavioral interventions
8. Primary clinical diagnosis is selective mutism.
9. History of recent physically aggressive behaviors that have caused harm to other children
10. Sibling of a child who has participated or is currently participating in this protocol

Parents of children with clinical anxiety symptoms

Inclusion criteria

1. Fluent in English (note: Participant may be bilingual, but must be able to speak and understand fluent English to participate in Questionnaire study)
2. Parent lives with child at least 50% of time
3. Has access to internet and webcam
4. Written informed consent for self and for their child

Exclusion criteria

1. Under 18 years of age
2. Not able to meet scheduling demands of the study

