2. Participants may experience some discomfort upon removal of the electrophysiological equipment – specifically, facial electrode sensors.

To minimize risk: Participants will be informed that facial electrode sensors are similar to Band- Aids, to help guide their preference for removal.

Risks Associated with Behavioral Battery

1. Some children may experience some emotional discomfort or apprehension when engaging in the behavioral "potential threat task." During this task, children enter a room and are asked to approach a covered terrarium. When they get close, the cover is lifted by the experimenter to reveal a benign object (e.g., a tissue box). This task elicits uncertainty during approach.

To minimize risk: Particular care will be taken during debriefing of the potential threat task. Child participants will be reassured that the covered object is not threatening immediately after its presentation. If a child becomes overly distressed, the protocol may be interrupted and parent can interact with child to provide comfort. The task may be

ended early if the child becomes tearful or otherwise highly distressed. All participants will be given a 5-minute free play with the parent immediately after the fear task to regulate and debrief.

Risks Associated with Intervention Training

1. Risks of participating in the camp are minimal, and include boredom or frustration with training tasks, similar to experiences children may encounter in a day-to-day school environment.

To minimize risk: Participants will be allowed breaks throughout daily training. Study team members conducting the camp will have experience with young children and be closely supervised by [name].

2. As with any group activity with children, there is always the possibility of unpredictable behavior, which could cause children discomfort or distress.

To minimize risk: Every precaution will be taken to ensure the safety of all children participating in the camp. This includes reserving the right to ask children to discontinue participation if there is reasonable concern for unsafe behavior.

Risks Associated with COVID-19

1. Travel to CU for the onsite sessions may increase risk of exposure to COVID-19.

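### The primary arm comparison carries no camp-group or data-source term although both arms are delivered in groups; if each camp runs one arm and outcomes correlate within camps, a child-level test at 5% is too liberal

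*Combined protocol and SAP*

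**What the plan says.** Delivery is in groups. Section 5 has: "Both Kidpower-Structured Games and -CLP conditions will be delivered to small groups of clinically anxious preschoolers by study team members". Section 6 describes a session: "Regardless of condition, children will begin with a group welcome activity", after which children do "intervention exercises with their camp counselor, then come back together for a final group activity". Section 5 lists the shared exposures that the comparator is meant to control, among them "interaction with new children during activities; c) separation from parents; and d) time spent with new adults".

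Section 6 randomizes participants and states the primary analysis in one sentence: "Primary analyses will test for group mean differences in neurophysiological and behavioral indices of EC", pre to post, between children by assigned arm. The word group there means arm. Later in Section 6 the data from this site (up to 20 children) "will be collapsed together with data collected using the same study protocol" at Michigan State (71) and NYSPI (43).

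No part of the document names a model, a camp, counselor or source term, a camp size, a number of camps, an ICC or an alpha level.

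**The concern.** Randomizing children individually does not make their outcomes independent once they are treated together. Children in one camp share peers, staff and the course of the sessions. If a camp delivers only one arm, any camp effect falls wholly within that arm and adds variance to the arm contrast that a child-level standard error does not count. Aim 1 would then be tested at more than the nominal level, with intervals that are too narrow. The active comparator balances the type of exposure between arms, but it does not remove correlation within a camp.

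Leaving out data source is a smaller and different matter. It costs precision when arms are balanced within source, and it can bias the contrast only when they are not. The document does not describe allocation by source.

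**Working it through.** The plan contains no alpha, power or sample-size figure, so there is nothing of its own to reproduce.

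**Inputs from the document (Section 6).** 71 + 43 = 114 earlier children; with up to 20 more, at most 134.

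**Assumed inputs.** Two-sided 5%, 1:1 allocation, one-arm camps of m = 4, 6 or 8, ICC 0 to 0.10, no missing data.

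**Type I error of a child-level test.** DEFF = 1 + (m − 1) × ICC; true alpha = 2 × [1 − Φ(1.96/√DEFF)]. Example: m = 6, ICC 0.05 gives DEFF = 1.25, 1.96/√1.25 = 1.753, and alpha = 8.0%.

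| m | ICC 0 | 0.01 | 0.02 | 0.05 | 0.10 |
|---|---|---|---|---|---|
| 4 | 5.0% | 5.3% | 5.7% | 6.8% | 8.6% |
| 6 | 5.0% | 5.6% | 6.2% | 8.0% | 11.0% |
| 8 | 5.0% | 5.8% | 6.6% | 9.2% | 13.3% |

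Simulation under the null (40,000 runs, 67 per arm, child-level t-test) gave 6.7%-9.1% at ICC 0.05, 8.3%-13.2% at 0.10, and about 5% at ICC 0.

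**Two variations.**
- If the cluster is a counselor subgroup of 2-3 children, the formula gives 5.6%-6.2% at ICC 0.05 and 6.2%-7.4% at 0.10.
- If camps mix the arms equally, the same simulation gave 4.3%-4.6% at 0.05 and 3.8%-4.0% at 0.10, so there is no inflation.

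**Does the remedy hold its level?** Simulations used sources of 71, 43 and 20, about 1:1 within source, one-arm camps of about 4, 6 and 8, and ICC 0, 0.05 and 0.10.
- Camp means with source fixed effects rejected 4.7%-5.3% of true nulls, weighted by camp size or not.
- A REML random-intercept model with source fixed effects and Satterthwaite degrees of freedom rejected 2.6%-4.0% at ICC 0 and 3.6%-4.7% at 0.05-0.10. It never exceeded 5%, but it is conservative when the ICC is zero.

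**Precision cost.** Degrees of freedom = camps − 4 (intercept, arm, two source terms). Widening = t(0.975, df) × √DEFF / t(0.975, 132) − 1, with t(0.975, 132) = 1.978. Camps = 134/m, rounded down.

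| m | camps | df | t | ICC 0 | 0.05 | 0.10 |
|---|---|---|---|---|---|---|
| 4 | 33 | 29 | 2.045 | 3% | 11% | 18% |
| 6 | 22 | 18 | 2.101 | 6% | 19% | 30% |
| 8 | 16 | 12 | 2.179 | 10% | 28% | 44% |

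From the noncentral t, the difference detectable with 80% power is 0.49 SD when clustering is ignored and 0.54-0.69 SD at ICC 0.05-0.10.

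**The case against.** The strongest reply is that the inflation needs three things that the document does not state: one arm per camp, a positive ICC, and a child-level test at 5%. That is correct, and it is why the result is conditional. A reader might infer that the plan commits to an unadjusted t-test, but it names no test. A reader might also take one-arm camps as settled. Section 5 and the description of the comparator in Section 6 make that the more natural reading. However, the session description in Section 6, with children coming back together after counselor-led exercises, does not exclude a single camp with arm-specific subgroups.

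The evidence for correlation is also limited. The document gives neither a staff ratio nor the number of children per counselor, so one-to-one exercise work is possible. The warning about unpredictable behavior in Section 11 concerns distress, and the scheduling options in Section 6 are not said to differ by camp. Neither supports an ICC for EEG or effortful-control outcomes.

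The ICC may well be low. The outcome is pre-to-post change, and measurement error at both visits pulls the ICC of change down. Lost data also shrink the analysed camps: with an assumed 20%-30% unusable, the formula gives 6.0%-8.2% at ICC 0.05 and 7.1%-11.4% at 0.10.

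Finally, Section 6 is headed with a one-page limit. That may explain the brevity, but no other analysis text fills the gap. What stands is that the stated comparison, followed literally on pooled data, is at child level, and nothing in the plan rules that out.

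**Conclusion.** The concern holds in conditional form. The omission of camp and source terms is a fact of the text. With one-arm camps of 4-8, a nominal 5% child-level test of Aim 1 would have a true type I error of about 5.3%-6.6% at ICC 0.01-0.02, rising to 8.6%-13.3% at 0.10. At ICC 0 nothing is wrong, and with mixed-arm camps the error runs slightly the other way. Camp size, ICC, allocation and alpha are all assumed, so these are ranges and not findings about this trial.

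A reader might extend the point to Aims 2 and 3, but the figures do not support that. If camp effects on the two related variables are independent, DEFF = 1 + (m − 1) × ICCx × ICCy. That gives 1.0075 and 5.1% for m = 4 with both ICCs 0.05, and 1.07 and 5.8% for m = 8 with both 0.10.

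This should be fixed before analysis; confidence is medium.

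**What to change.** For the Aim 1 primary analysis only:

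1. State whether each camp delivers one arm, and whether the cluster is the whole camp or a counselor subgroup.
2. Prespecify an analysis that respects it. With one-arm camps, either compare camp means between arms with data source as a fixed effect, or fit a child-level mixed model with a camp random intercept, source fixed effects and small-sample degrees of freedom. If camps mix arms, use the second form, since whole-camp means then do not separate the arms.
3. Report the estimated ICC.
4. Check now whether camp membership can be recovered for the 114 earlier children; the document does not say. If it cannot, keep the source term and show the primary result over a range of ICCs.

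The work is mainly wording plus that data check. The statistical cost at ICC 0 is intervals about 3%-10% wider with camp means, or 8%-18% wider with the REML mixed model. At ICC 0.05-0.10 intervals are about 11%-44% wider, but there the narrower child-level interval would be wrong.

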4. SPECIFIC AIMS/HYPOTHESES

Aim 1: Confirm that Kidpower-Structured Games engages neural and behavioral markers of EC. We hypothesize that Kidpower-Structured Games will produce greater increases in neurophysiological and behavioral markers of EC than Kidpower-Child-Led Play (CLP, active comparator).

Aim2: Assess the relationship between pre- to post-Kidpower-Structured Games change in neurobehavioral markers of EC and change in clinically significant anxiety. We hypothesize that increases in neurophysiological and behavioral measures of EC will relate to reductions in clinically significant anxiety from pre-to-post Kidpower- Structured Games. Exploratory analyses will examine the moderating effects of baseline threat reactivity on the relation between pre- to post-treatment increase in EC and reduction in anxiety severity.

Aim 3: Explore dosing effects of Kidpower-Structured Games on behavioral EC targets and anxiety symptoms. We hypothesize that greater at-home practice of Kidpower-Structured Games exercises will relate to greater engagement of neural and behavioral markers of EC targets and greater reduction in anxiety symptoms. Dosage will be assessed by weekly parent report on child practice of EC exercises at home (frequency, duration).

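### Aim 1 reads as an unadjusted comparison of change between arms; stating adjustment for the time-1 value is a nearly free and usually more precise choice

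*Combined protocol and SAP*

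**What the plan says.** Section 6 (Research Design and Methods) describes the primary analysis in a single sentence: "Primary analyses will test for group mean differences in neurophysiological and behavioral indices of EC from time 1 (pre-intervention) to time 2 (post-intervention"), comparing the two randomized arms. Aim 1 in section 4 says that the structured games "will produce greater increases in neurophysiological and behavioral markers of EC" than the comparator. No model is named, and no adjustment for the time-1 value of an index is mentioned.

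The time-1 values will exist. Section 6 states "Before and after the 4-week intervention, a multi-level assessment will be completed", covering EEG and behavioral tasks, and under Behavioral Measures "Pre/post behavioral tasks are drawn from widely employed temperament protocols".

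Three other statements bear on the point:

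- Section 5 notes that both "conditions will be delivered to small groups of clinically anxious preschoolers", so outcomes may vary between camps.
- Section 6, under Error Related Negativity, says "The number of NoGo errors and response times (RTs) to Go trials will also be considered in NP analyses", without naming the visit. The Zoo task that yields these measures is called a "paradigm assessing effortful control, has been found to reliably elicit ERN in preschoolers".
- The secondary analyses are separate: "Secondary analyses will test relationship of changes in neurophysiological targets with change in EC behaviors and change in anxiety severity".

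**The concern.** Where the arms are randomized and the outcome is measured before and after, a comparison of change and a comparison of the time-2 value adjusted for the time-1 value estimate the same arm effect. Change fixes the coefficient on the time-1 value at 1. Adjustment estimates it, and so usually gives a smaller standard error.

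Precision matters because the sample is bounded. Section 6 pools 71 children from Michigan State and 43 from the New York State Psychiatric Institute with up to 20 at Columbia, so the ceiling is 71 + 43 + 20 = 134. Section 8 counts Columbia children as enrolled before eligibility is confirmed, so the analysable number may be lower. Michigan State has finished enrolling, so lost precision could not readily be recruited back.

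There is a related gap. If NoGo errors or Go response times enter the arm comparison as covariates, their visit matters. Time-2 performance is measured after randomization on a task that assesses the construct being trained, so adjusting for it could remove part of the effect under test.

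**Working it through.** The plan states no power, effect size, SD or correlation for this analysis, so there is no figure of its own to reproduce.

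**Assumed inputs.** Time-1 SD is 1 and time-2 SD among children is k. The pre-post correlation is ρ. There are m children per camp, and camp variance arising after baseline is a share c of time-2 individual variance. Arms are equal and data complete.

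**Per-child variance of the arm contrast (large sample)**

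- Change: 1 + k² − 2ρk + mck²
- Adjusted: k²(1 − ρ²) + mck²
- Change minus adjusted: (1 − ρk)², which is zero or positive. Camp variation arising after baseline adds the same amount to both, so it dilutes the relative gain.

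**Equal SDs (k = 1), adjusted / change**

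| Setting | ρ = 0.3 | ρ = 0.5 | ρ = 0.7 |
|---|---|---|---|
| c = 0 | 0.91/1.40 = 0.650 | 0.75/1.00 = 0.750 | 0.51/0.60 = 0.850 |
| m = 4, c = 0.05 | 1.11/1.60 = 0.694 | 0.95/1.20 = 0.792 | 0.71/0.80 = 0.888 |
| m = 6, c = 0.05 | 1.21/1.70 = 0.712 | 1.05/1.30 = 0.808 | 0.81/0.90 = 0.900 |
| m = 6, c = 0.10 | 1.51/2.00 = 0.755 | 1.35/1.60 = 0.844 | 1.11/1.20 = 0.925 |
| m = 8, c = 0.10 | 1.71/2.20 = 0.777 | 1.55/1.80 = 0.861 | 1.31/1.40 = 0.936 |

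Without camp variation the variance reduction is 35%, 25% and 15%. Across the camp settings it is about 31-22%, 21-14% and 11-6%. Simulation with 22 camps of 6 gave ratios of 0.646, 0.757 and 0.850 at c = 0 and 0.711, 0.815 and 0.909 at c = 0.05, with both estimators unbiased.

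**Where the gain is small**

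- ρ = 0.9, k = 1, m = 6: 0.49/0.50 = 0.980 at c = 0.05 and 0.79/0.80 = 0.988 at c = 0.10, a gain of 1-2% (5% with no camp variation, 0.19/0.20).
- ρ = 0.7, k = 1.25, m = 6: 0.797/0.8125 = 0.981, 1.266/1.281 = 0.988 and 1.734/1.750 = 0.991 at c = 0, 0.05 and 0.10, again 1-2%.

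**Where it can reverse.** Suppose camps already differ at baseline, with variance c, and the difference persists unchanged. Change then cancels the camp term and has variance 2(1 − ρ), with ρ now the within-camp correlation. The adjusted slope is β = (ρ + c)/(1 + c), and the adjusted variance is (ρ − β)² + (1 − ρ²) + mc(1 − β)².

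- m = 8, c = 0.20, ρ = 0.5: β = 0.583; 0.007 + 0.750 + 0.278 = 1.035, against 1.000.
- m = 8, c = 0.20, ρ = 0.7: β = 0.750; 0.0025 + 0.510 + 0.100 = 0.6125, against 0.600, ratio 1.02.
- m = 6, c = 0.10, ρ = 0.7: β = 0.727; 0.001 + 0.510 + 0.045 = 0.555, against 0.600, ratio 0.93.

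Simulations of the first two settings gave ratios between 1.02 and 1.07. At m = 6 and c = 0.10 adjustment still won.

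**Time-2 performance as covariate (illustration only).** The shift in the estimate is slope × effect of training on the covariate. If training lowers time-2 NoGo errors by 0.3 to 0.5 SD, and the ERN index improves by 0.2 to 0.3 SD per SD fewer errors, the shift is 0.2 × 0.3 = 0.06 to 0.3 × 0.5 = 0.15. A true effect of 0.40 SD would be estimated at 0.34 to 0.25. With time-1 errors it stays at 0.40.

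**The case against.** The strongest reply is that the plan never commits to an unadjusted analysis. The sentence sits under a heading limited to one page, and it also fits an arm-by-time mixed model or a baseline-adjusted model. A reader might infer that the trial will use a raw change score, or that its result would be biased. The documents support neither: adjustment is not excluded, and an unadjusted comparison of change is unbiased under randomization and answers Aim 1 as worded. What stands is that the wording most naturally describes change, and that a usually better choice is available at almost no cost.

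Second, every input to the size is assumed, and the gain runs from 35% down to nothing. That stands, so no power figure is offered. A reader might also infer that adjustment can never lose. That is a large-sample result which requires camp variation to arise only after baseline, and section 6 does not say how children are grouped into camps.

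Third, regressing time-2 on time-1 values drops children whose time-1 EEG is unusable, whereas a mixed model may keep them. This is right, and the fix allows for it.

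Fourth, the plan says only that task performance will be considered, because it can affect ERN amplitude. It does not say that time-2 performance will be a covariate in the arm comparison, so that part is conditional. Time-1 performance also cannot show how time-2 performance affects time-2 ERN; a labelled sensitivity analysis can serve that purpose.

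Finally, the documents do not say whether arm comparisons have already been run on the earlier data, so the model may not be settable ahead of all of them.

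**Conclusion.** The point holds as an inexpensive improvement to an under-specified analysis; it is not an error that invalidates the trial. As worded, Aim 1 compares change between arms with no stated adjustment for the time-1 value, and adjusting would usually be more precise. A worthwhile gain depends on a moderate pre-post correlation, similar SDs at the two visits and camp differences that arise mainly after baseline. The correlation may also differ between ERN, ICPS and the behavioral indices. If the team already intends adjustment, precision is unchanged and the benefit is only that the choice is on record. Confidence is medium, because the reading rests on one sentence and the size on assumed inputs.

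**What to change.** In section 6, state that each Aim 1 EC index measured at both visits is analysed as the time-2 value by arm, adjusted for the time-1 value of the same index. Settle this before any further or pooled arm comparison is run. Add that children with unusable time-1 data stay in the analysis, for example through a longitudinal model that constrains the two arms to a common baseline mean.

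Under Error Related Negativity, state that if NoGo errors or Go response times are covariates in the primary arm contrast, their time-1 values are used, and that any analysis using time-2 performance is labelled a sensitivity analysis.

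Leave Aim 2 and the secondary change-on-change analyses as they are. How camp enters the model is a separate question that baseline adjustment does not settle.

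The cost is a few sentences and one degree of freedom for the baseline term. No new data are needed, since both assessments are already scheduled.
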